Last Updated: 2.24.2023

ARENA LABS - IMPROVING CLINICIAN WELL BEING

IRB00090882

NCT05653700

IRB Approval Date: 03.01.2023

Atrium Health | Arena Labs Research Protocol

Project Title

The effect of an asynchronous coaching platform on measures of physiological resilience, professional fulfillment, burnout, self-valuation, and overall satisfaction in Atrium Health Sanger Heart and Vascular Institute Surgery, Emergency Department, and Pulmonary Critical Care Physicians and Advanced Practice Providers.

Principal Investigator and Co-Investigator Information

Principle Investigator: [name]

Research Question/Hypothesis

What is the effect of educational content; data feedback and monitoring; and tailored coaching touchpoints provided through an asynchronous coaching platform on measures of physiological resilience, professional fulfillment, burnout, self-valuation, and overall satisfaction in full time clinical providers?

Objectives

The primary objective of this study will be to determine the efficacy of the asynchronous performance coaching platform, Arena Strive at changing measures of physiological resilience, professional fulfillment, burnout, and self-valuation in full time clinicians. The anticipated **primary outcome** will be an improvement in measures related to clinician resilience including self-reported professional fulfillment and self-valuation; factors measured by the WHOOP biometric device: Heart rate variability (HRV), resting heart rate (RHR), time spent in bed, sleep quality, sleep consistency, reduction in "sleep debt"; and a reduction in burnout. Expected **secondary outcomes** include an overall high level of self-reported acceptance, satisfaction, and feasibility of the Arena Strive Platform.

- Primary outcome: Increases in physiological and self-reported measures of resilience / decreases in burnout measures.
- Secondary outcome: Feasibility, acceptance, satisfaction of Arena Strive platform

Background to Research Questions

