Throughout the 12 week intervention period, **participant engagement** within the Arena Strive app will be collected including data points relating to videos/audio watched or listened to, content favorited, or user activities completed. Modifiable activities collected via the Arena Strive Platform include light exposure, light restriction, sleep hygiene, meal timing, and activation and deactivation techniques (yoga nidra, physiological sigh, super O2 breathing).

Self-reported data will also be collected relating to the participants ability to adapt to stress, rest and recover from stress, and self-awareness around these two constructs. WHOOP data, engagement within the Arena Strive app, and self-reported stress adaptability, rest and recovery, and self-awareness will be collected continually throughout the intervention period. The additional self-reported outcomes: professional fulfillment, burnout, self-valuation, and overall satisfaction will be collected by means of an in-app survey at key benchmark moments throughout the intervention period: once at intervention start, again at week 6 following the first phase of the Arena Strive intervention, then again at week 12 following the completion of the experimental intervention period. Participants in the control cohort will follow this same time frame with respect to self-reported surveys. All self-reported data within the control cohort will be collected via identical surveys hosted on Typeform, the web-based surveying platform.

The experimental intervention, 'Arena Strive', will be conducted through the Arena Strive app, self-described as "Healthcare's First Performance Coach". This second-generation platform provides frontline clinicians with a comprehensive journey to access the tools, training, and technology used by other high-pressure fields to increase performance and enhance resilience. Strive uses a dynamic, interactive content platform to bring frontline clinicians the lessons learned, tools, and tailored instruction of world-class performers from elite military, professional athletes, and creative performers. The design will test the effect on measures of professional fulfillment and burnout; self-valuation; satisfaction; and feasibility in full-time NHS clinicians.

Intervention

The experimental intervention employed in this study will be a 12-week, multi-phased approach involving asynchronous learning and coaching experience (6 weeks), and exploration phase (6 weeks).

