Participant Consent: All participants involved in this study will be required to provide written consent to participate. Participants will be asked to consent to the collection of self-reported data provided through in-app and digital surveys as well as biometric data collected through the WHOOP device. A copy of the written consent form is included in the appendix. Spanish language consents will be made available upon request.

Equipment/Supplies/Services

All equipment, services, and supplies related to the study intervention will be provided by Arena Labs, and WHOOP. All equipment, services, and supplies related to the recruitment of study participants will be provided by the Atrium Health team.

Data Collection

All study data will be collected via an in-app or online survey, through app interactions, or through the WHOOP wearable biometric device. Data collection for the control cohort will mirror that of the experimental group in both frequency and content with a select few exceptions. Control cohort participants will not receive questions relating to feasibility and satisfaction, and self-reported data will be collected via online surveys hosted on Typeform. A breakdown of the primary and secondary outcome variables are summarized below.

		Outcome Variable	Instrument	Collection Method
Primary Outcomes	Self Reported	Professional Fulfillment & Burnout	Stanford Professional Fulfillment Index (PFI)	Onboard, midpoint, and exit Survey
		"Gold standard" for measuring burnout	Maslach Burnout Inventory (MBI)	Onboard, midpoint, and exit Survey
		Self Valuation	Stanford Self Valuation Scale	Onboard, midpoint, and exit Survey
	Biometric Data	HRV	WHOOP Strap	Continuous
		SWS %	WHOOP Strap	Continuous
		REM %	WHOOP Strap	Continuous
		RHR	WHOOP Strap	Continuous
		Awake Time	WHOOP Strap	Continuous
		Light Sleep Duration (%)	WHOOP Strap	Continuous

		Sleep Disturbances	WHOOP Strap	Continuous
		Sleep Debt	WHOOP Strap	Continuous
		Sleep Consistency	WHOOP Strap	Continuous
Secondary Outcomes	Self-reported	Satisfaction	Client Satisfaction Questionnaire-8 (CSQ-8)	Exit Survey
		Feasibility/Adherence	NA	In-app Survey & app engagement

Data Analysis

- We will use t-tests in SPSS to compare the primary outcome measures across the experimental and control groups.

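### Satisfaction is surveyed three times in one section and at exit only in another; on the exit-only schedule it would be seen mainly in completers and is likely, though not certain, to be overestimated

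*Combined protocol and SAP*

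**What the plan says.** **Study design (Methodology).** Satisfaction is grouped with three other self-reported outcomes: "professional fulfillment, burnout, self-valuation, and overall satisfaction will be collected by means of an in-app survey at key benchmark moments". Those moments are "once at intervention start, again at week 6 following the first phase of the Arena Strive intervention" and "then again at week 12 following the completion of the experimental intervention period".

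**Data Collection, outcome table.** The only satisfaction instrument is the "Client Satisfaction Questionnaire-8 (CSQ-8"), and its collection entry is the exit survey alone. The self-reported primary scales in the same table carry a different entry: "Onboard, midpoint, and exit Survey". Feasibility/adherence has its own row and is collected by in-app survey and app engagement.

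**Who is asked.** Data Collection states: "Control cohort participants will not receive questions relating to feasibility and satisfaction". Satisfaction is therefore a single-arm measure.

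**Expected result.** Objectives anticipates "an overall high level of self-reported acceptance, satisfaction, and feasibility of the Arena Strive Platform". No numerical threshold for a high level is given, and Data Analysis describes no analysis of satisfaction. Study design labels the analysis per protocol without defining that population.

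**The concern.** Two sections give different schedules for one secondary outcome, and staff cannot follow both. The choice between them affects the result. On the exit-only schedule the rating comes after the 12-week programme has ended. No survey at discontinuation is described, and no denominator is fixed for satisfaction. Clinicians who give up the programme early, perhaps because it did not help them, are the people most likely to be missing from the rating. A per-protocol analysis would tend to leave them out even if they did answer.

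For a self-directed coaching app, the opinion of those who abandon it is a large part of the question of acceptability. A favourable satisfaction figure could be reported while a sizeable share of the assigned clinicians had gone unheard.

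**Working it through.** **Step 1: compare the schedules.**

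| Source | What is scheduled | When |
|---|---|---|
| Study design | Overall satisfaction, instrument not named | Start, week 6, week 12 |
| Data Collection table | CSQ-8 | Exit survey only |
| Same table, PFI, MBI and Self Valuation rows | Primary self-reported scales | Onboarding, midpoint, exit |

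The table distinguishes three-time-point scales from an exit-only scale, so its satisfaction entry does not look like shorthand for all three surveys. It lists no second satisfaction measure to which Study design could be referring. The conflict stands without any assumption.

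**Step 2: can early stoppers be reached?** Study design delivers the experimental arm's surveys in the app. Setting places all data collection in the app and the strap. Data Collection allows online surveys in general but assigns Typeform to the controls. No section says whether someone who has stopped receives the exit survey.

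**Step 3: inputs.** The documents give a maximum of 100 participants randomised 2:1, so the programme arm is 100 × 2/3 = 66.7, about 67. They give no stopping rate, no satisfaction rate and no CSQ-8 cut-off, so there is no plan figure to reproduce. Every rate below is an assumption.

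**Step 4: bounds that assume nothing about the views of stoppers.** Let d be the share unrated and p the proportion satisfied among raters. The whole-arm proportion lies between (1 − d)p and (1 − d)p + d. With p = 85%:

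- d = 10%: 76.5% to 86.5%
- d = 20%: 0.80 × 85% = 68%, to 68% + 20% = 88%
- d = 30%: 59.5% to 89.5%
- d = 40%: 51% to 91%

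At d = 20% the whole-arm figure could be up to 17 points below the reported 85%, but only 3 points above it.

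**Step 5: overstatement under assumed views of stoppers.** Overstatement = d × (p among completers − p among stoppers). With 85% of completers satisfied, in percentage points:

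| Share unrated | Stoppers 85% | Stoppers 60% | Stoppers 40% | Stoppers 20% |
|---|---|---|---|---|
| 10% | 0 | 2.5 | 4.5 | 6.5 |
| 20% | 0 | 5 | 9 | 13 |
| 30% | 0 | 7.5 | 13.5 | 19.5 |
| 40% | 0 | 10 | 18 | 26 |

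The sign reverses if stoppers are the more satisfied group. With completers at 60%, stoppers at 85% and d = 20%, the result is 0.20 × (60 − 85) = −5 points.

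**Step 6: what a week-6 rating would add.** Suppose half of the eventual stoppers answer at week 6, 40% of them are satisfied, and completers are at 85% then too. With d = 20%, the week-6 figure is (0.80 × 0.85 + 0.10 × 0.40)/0.90 = 0.80. The whole-arm figure is 0.80 × 0.85 + 0.20 × 0.40 = 0.76. The overstatement falls from 9 to 4 points. At d = 40% the same calculation gives 0.59/0.80 = 0.738 against 0.67, so it falls from 18 to 6.8 points. A midpoint rating reduces the problem but does not remove it.

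**The case against.** The strongest reply is that the conflict may be only loose wording. Study design does not name the CSQ-8, and rating a programme at its start means little. The instrument-level table may therefore be the intended schedule. That is plausible, but it leaves the text contradictory and leads to the exit-only schedule, where the question about stoppers arises.

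A reader might infer four stronger things that the documents do not support:

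- **That early stoppers never rate the programme.** The documents are silent on this, and silence is not a rule. Data Collection permits online surveys, consent covers digital surveys, and Identified Risks lets a participant give up the device and keep the educational content. Leaving the app or the strap does not by itself make someone unreachable.
- **That the figure is biased upward by a known amount.** The size depends entirely on assumed rates. It can be zero, large or negative.
- **That feasibility fails in the same way.** App engagement is collected throughout the intervention, so abandonment should show there.
- **That the lack of a control rating hides the selection.** Untreated controls have no programme to rate. Study design does say "Participants in the control cohort will follow this same time frame with respect to self-reported surveys", but leaving them out of the satisfaction items is sensible.

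It is also fair to say that this is one uncontrolled secondary measure and that no primary comparison is affected. A survey triggered by stopping would need a way to detect stopping in an asynchronous app, and carrying the last rating forward would mix time points. Neither is needed for the fix below.

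**Conclusion.** The concern holds in a limited form. The schedule conflict is established from the text alone. On the exit-only reading, no stated means exists for early stoppers to rate the programme, so the result would describe mainly completers. Overestimation is the likely direction, on the assumption that those who stop are on average less satisfied. The documents contain no data on this.

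No size can be stated as a finding. The most that can be said is conditional: with 85% satisfied among raters and 20% unrated, anything from 68% to 88% of the arm is possible. The point concerns satisfaction. It should be corrected before the result is reported, but it does not threaten the primary outcomes.

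**What to change.** 1. Reconcile Study design with the outcome table. Give the CSQ-8 at the existing week-6 midpoint survey and at the week-12 exit survey. Drop satisfaction from the start survey, where there is nothing yet to rate.
2. Send the exit survey to everyone assigned to the programme, whether or not they still use the app, by online link if needed. State this in Data Collection and align Setting, which now confines data collection to the app and strap.
3. Report week-6 and week-12 satisfaction separately, each with responders out of all assigned (about 67), whatever the per-protocol population turns out to be.
4. Add a sensitivity figure counting non-responders as not shown to be satisfied. In the illustration this is 0.80 × 85% = 68%. It requires a CSQ-8 cut-off fixed in advance.
5. Report the proportion who stopped beside the satisfaction figure, with stopping defined in the plan.

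The cost is a wording change, one more short questionnaire at a survey already scheduled, and an online link of the kind already used for controls. Participants give a few extra minutes. The satisfaction figure will probably be less favourable. Those who stop before week 6 and ignore the link will still be unrated, and the denominator and sensitivity figure are there to make that visible.

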Recent literature has found that burnout is highly prevalent among healthcare professionals, affecting between 40-60% of physicians. [1] The added stressors of the COVID-19 pandemic have also been associated with high rates of multidisciplinary healthcare professional burnout, depression and anxiety, especially among women, nurses, and those working in hospital environments.[2-3] Mental health disorders are also prevalent among health care workers. In a study of 4833 physicians, 41.7% screened positive for depressive symptoms and 6.9% reported having suicidal ideation in the previous year, of whom 27% reported that they would probably or definitely not seek help.[4] The healthcare professionals most in need of care and burnout prevention modalities are those least likely to seek support, with a perceived stigma associated with seeking help.[5] These findings contribute to the mounting body of evidence suggesting there is a significant unmet gap in this vulnerable population.

Healthcare clinicians work in a high-stress environment that requires quick decision making and high levels of both mental and physical acuity. Like other performance careers, a clinician's own mental and physical states are key to their ability to take optimal care of their patients. However, despite the

Last Updated: 2.24.2023

similarities shared with these other performance careers, performance coaching, well-being interventions, and other burnout prevention initiatives are commonly perceived as either ineffective, or out of reach to the health professional workforce due to time restraints, lack of knowledge, or pre-existing stigmas around help seeking. Arena Strive and WHOOP aim to address these barriers by democratizing performance coaching with a seamless asynchronous coaching experience at the clinicians fingertips.

METHODOLOGY

Study design

This study is a prospective randomized controlled longitudinal crossover design with a per protocol analysis integrating one sensor (WHOOP, inc Platform) and one educational intervention (Arena Strive Platform). The **WHOOP** sensor collects **data** on heart rate (HR), heart rate variability (HRV), and sleep data, and will be worn by all participants in the experimental intervention. Participants will be asked to wear the biometric sensor for 12 weeks but will have optional access to the device for a total of 24 weeks.

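### Twelve outcomes are labelled primary, but the plan sets no alpha, multiplicity rule or success rule, and names no primary survey time point or sensor contrast

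*Combined protocol and SAP*

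**What the plan says.** The Objectives section puts the primary outcome as "Primary outcome: Increases in physiological and self-reported measures of resilience / decreases in burnout measures". The longer list just above it includes "time spent in bed, sleep quality, sleep consistency" and ends with "and a reduction in burnout". It does not say how many of these must improve.

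The Data Collection table groups 12 rows under primary outcomes:
- Three survey instruments: the Professional Fulfillment Index (PFI), whose row covers both fulfillment and burnout, the Maslach Burnout Inventory (MBI) and the Self Valuation Scale.
- Nine WHOOP variables: HRV, SWS %, REM %, RHR, awake time, light sleep, sleep disturbances, sleep debt and sleep consistency.

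Surveys are taken "once at intervention start, again at week 6 following the first phase of the Arena Strive intervention", and again at week 12. The table calls these onboard, midpoint and exit surveys.

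Data Analysis has five bullets. The first reads "We will use t-tests in SPSS to compare the primary outcome measures across the experimental and control groups". The others cover dose correlations, mixed models over time for sleep, HRV and RHR by group, dose mixed models, and mediation models. None of them, and no other section, gives an alpha, a hierarchy, a multiplicity adjustment or a success criterion.

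**The concern.** The stated primary objective is to determine efficacy, so the plan must say which result would count as efficacy. It does not. Nothing in it prevents one unadjusted favourable result among several from being reported as the objective met. Equally, nothing prevents the objective from being read as needing every outcome to improve. The two readings have opposite problems, inflated error in one and possibly low power in the other, and the choice could be made after the data are seen.

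The set of primary outcomes is not stable either. Time in bed is in the Objectives list but is not a table row. The mediation bullet treats sleep and recovery as a step on the way to the primary measures, although the table makes the sleep variables primary. The Study Design summary, "The design will test the effect on measures of professional fulfillment and burnout; self-valuation; satisfaction; and feasibility in full-time NHS clinicians", names no sensor outcome. For the surveys, no time point is named as primary. For the sensor data, which are modelled over time, no single model contrast is named.

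**Working it through.** The plan gives no error rate, power or effect size, so there is no figure of its own to reproduce.

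**Inputs from the protocol.** There are 3 + 9 = 12 primary rows. At most 100 participants are allocated 2:1, about 67 vs 33 (Study Participants).

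**Assumptions, not in the protocol.** Each test is two-sided at 0.05 (critical value c = 1.96). Tests share a common correlation ρ. For error rates, no outcome has a true effect. The four survey scores are PFI fulfillment, PFI burnout, one MBI score and self-valuation.

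**1. One significant result suffices.** With independent tests, the chance of at least one false positive among k tests is 1 − 0.95^k in either direction and 1 − 0.975^k in the favourable direction:
- k = 3: 1 − 0.857 = 14.3%; favourable 1 − 0.927 = 7.3%
- k = 4: 1 − 0.815 = 18.5%; favourable 1 − 0.904 = 9.6%
- k = 12: 1 − 0.540 = 46.0%; favourable 1 − 0.738 = 26.2%

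With correlation ρ, the chance is 1 − ∫ φ(u) [Φ((c − √ρ·u)/√(1−ρ)) − Φ((−c − √ρ·u)/√(1−ρ))]^k du. The second Φ term is dropped for the favourable direction. Numerical integration gives:

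| Tests | ρ = 0 | ρ = 0.5 | ρ = 0.7 |
|---|---|---|---|
| 3 instruments, either direction | 14.3% | 12.5% | 10.9% |
| 3 instruments, favourable | 7.3% | 6.3% | 5.5% |
| 4 scores, either direction | 18.5% | 15.6% | 13.0% |
| 4 scores, favourable | 9.6% | 7.8% | 6.5% |
| 12 rows, either direction | 46.0% | 31.9% | 23.2% |
| 12 rows, favourable | 26.2% | 16.0% | 11.6% |

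The single-test values are 5% and 2.5%. The 12-row lines apply only if the table's label governs and controls supply sensor data.

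**2. All 12 must improve.** Error does not inflate. With no true effects, false success is below 0.1% at correlation up to 0.7. For power, I take a true improvement of 0.60 SD on every outcome, 67 vs 33, with all outcomes treated as t-tests. Simulation gives about 23%, 35% and 47% at ρ = 0.3, 0.5 and 0.7. It rises to about 54% at ρ = 0.8, and to about 57% at 0.65 SD with ρ = 0.7.

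**3. Cost of adjusting.** These figures use the noncentral t at 67 vs 33. Holm over four scores starts at 0.05/4 = 0.0125.
- Effect detectable with 80% power: 0.60 SD at 0.05; 0.72 SD at 0.0125.
- Power at 0.60 SD: 80% at 0.05; 61% at 0.0125.

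**The case against.** The best defence is that the analysis section implies a narrower plan. The bullets run in parallel: t-tests in SPSS and dose correlations on the primary measures, then mixed models in R and dose mixed models on sleep and recovery. With the mediation bullet and the Study Design summary, this suggests that the t-tests are for the surveys and that the sensor data form a separate strand. This is a fair reading, and it is why the survey figures come first. But the plan does not say so, the table says otherwise, and three or four unadjusted survey tests still exceed 5%.

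It can also be said that week 12 is plainly the endpoint, since it is the exit survey at the end of the intervention. That is the natural reading. Stating it would close the time-point gap for the surveys but would leave several primaries with no rule.

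A reader might take 46% as this trial's error rate. The documents do not support that. The figure needs independent tests, all 12 rows counted, and control-arm sensor data. On the last, the documents conflict. Study Design says the sensor "will be worn by all participants in the experimental intervention", Phase 2 of the Intervention section makes the device part of the intervention, and the Control Cohort paragraph gives controls none. Against that, the inclusion criteria require willingness to wear it, consent covers its data, control data collection is said to mirror the experimental arm, and the mixed models compare arms.

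A reader might also infer that requiring all 12 makes the trial more likely to fail than succeed. That holds for the lower correlations and the 0.60 SD assumed above, but not for stronger correlation or larger effects. The protocol gives no correlations, so none of the assumed values can be called the most plausible.

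**Conclusion.** The concern holds and should be fixed before analysis. As written, the plan allows several unadjusted tests of outcomes called primary, with no rule for success. If one survey result suffices, the false-positive risk is about 12.5% to 18.5%, or 6% to 10% in the favourable direction, against 5% and 2.5% for one test. These figures assume two-sided 0.05 per test, equal correlation of 0 to 0.5, and three instruments or four scores.

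The 12-row figures of 46% / 32% / 23% are conditional on the label and the control-arm sensor data. The all-must-improve power of about 23% to 47% is conditional on correlation 0.3 to 0.7 and 0.60 SD on every outcome. The conclusion depends on neither, because the missing rule alone leaves open what the trial can claim.

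**What to change.** Before any data are analysed:

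1. Name one week-12 primary outcome, tested at two-sided 0.05. Alternatively, name a small family of week-12 survey scores (for example PFI fulfillment, PFI burnout, one pre-specified MBI score and self-valuation) tested with Holm at an overall two-sided 0.05. For the family, success means at least one Holm-adjusted p below 0.05 favouring the intervention. Which outcome or outcomes to choose is for the sponsor.
2. Make everything else secondary, including week-6 comparisons and WHOOP variables not chosen, and report estimates with confidence intervals.
3. State which method applies to which outcome, and name one model contrast for each WHOOP variable.
4. Use the word primary for the same set in the Objectives, the table and the mediation bullet.

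This part is a change of wording. A single named primary costs no power. Holm over four scores raises the first-step detectable effect from 0.60 to 0.72 SD and lowers first-step power at 0.60 SD from 80% to 61%, if all 100 are analysed. The design is described as a "crossover design with a per protocol analysis", so fewer may count. With an assumed 80 analysed (53 vs 27), the detectable effect goes from 0.67 to 0.81 SD and power at 0.60 SD from 71% to 50%.

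Separately, reconcile the sections on whether controls wear the sensor during the 12 weeks. Without control sensor data the WHOOP between-group comparisons cannot be run, and putting that right may take more than wording.
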